4.2.1 Confirmation Scans

Verification of Response: To be assigned a status of CR or PR, changes in tumor measurements must be confirmed by consecutive repeat assessments that should be performed no less than 28 days after the criteria for response are first met. For this study, the next scheduled tumor assessment can meet this requirement.

4.3 Duration of Response

4.3.1 Duration of Overall Response

The duration of overall response is measured from the time measurement criteria are first met for CR/PR (whichever is first recorded) until the first date that progressive disease is objectively documented (taking as reference for PD the smallest measurements recorded on study), subsequent anti-cancer therapy (including tumor-directed radiotherapy and tumor-directed surgery) is initiated, or the participant dies, whichever occurs first.

The duration of overall complete response is measured from the time measurement criteria are first met for CR until the first date that progressive disease is objectively documented, subsequent anti-cancer therapy (including tumor-directed radiotherapy and tumor-directed surgery) is initiated, or the participant dies, whichever occurs first.

4.3.2 Duration of Stable Disease

If SD is the best overall response, the duration of SD is measured from the date of randomization until the criteria for progression are met, taking as reference the smallest sum on study (if the baseline sum is the smallest, this is the reference for calculation of PD), subsequent anti-cancer therapy (including tumor-directed radiotherapy and tumor-directed surgery) is initiated, or the participant dies, whichever occurs first..

APPENDIX 10 SUPPORTIVE CARE GUIDELINES FOR THE MANAGEMENT OF HAND FOOT SYNDROME (HFS)

Supportive Care Guidelines for the Management of Hand Foot Syndrome (HFS)

Management of HFS can begin before any symptoms occur. Several prophylactic measures may be taken to prevent or reduce the severity of HFS. Before therapy with begins, a full-body skin exam should be performed, with a special emphasis on hyperkeratotic areas on palms and soles and any deformities. Patients can receive a pedicure, using properly sterilized utensils, to remove any preexisting hyperkeratotic areas or calluses that may predispose them to developing HFS reaction. Patients should be advised to reduce the exposure of their hands and feet to hot water, either through dishwashing or hot baths and showers, because this is believed to exacerbate symptoms, and patients frequently report symptomatic relief with cold water.

Before initiating treatment:

- Check condition of hands and feet
- Suggest a manicure/pedicure, when indicated
- Recommend pumice stone use for callus or ‘rough spot’ removal

During treatment:

- Avoid pressure points
- Avoid items that rub, pinch, or create friction
- Apply non-urea based skin-hydrating creams liberally
- Keratolytic creams: Use sparingly and only to affected (hyperkeratotic) areas.

Urea-based creams:

- Salicylic acid 6%
- Alpha hydroxy acid (AHA) based creams
- Concentrations of approximately 5-8% provide gentle chemical exfoliation
- Apply liberally two times each day

Topical analgesics like lidocaine 2% should be considered for pain control

Topical corticosteroids like clobetasol 0.05% should be considered for patients with grade 2 or 3 hand-foot skin reaction. Avoid systemic steroids.

Cushions:

- Protect tender areas
- Use socks/gloves to cover moisturizing creams
- Wear well-padded footwear
- Use insole cushions or inserts (e.g., silicon, gel)
- Foot soaks with tepid water and Epsom salts

APPENDIX 11 SUPPORTIVE CARE GUIDELINES FOR THE MANAGEMENT OF DIARRHEA FOR CABOZANTINIB

Participants should be instructed to notify their physician immediately at the first signs of poorly formed or loose stool or an increased frequency of bowel movements. Guidelines for the evaluation and management of diarrhea are shown in [Table 1](#).

Administration of antidiarrheal/antimotility agents is recommended at the first sign of diarrhea as initial management. Some participants may require concomitant treatment with more than 1 antidiarrheal agent. When therapy with antidiarrheal agent does not control diarrhea to tolerable levels, cabozantinib should be temporarily interrupted or dose reduced. When the diarrhea is controlled, retreatment with cabozantinib may be acceptable per investigator decision.

In addition, general supportive measures should be implemented such as continuous oral isotonic hydration, correction of fluid and electrolyte abnormalities, small frequent meals, and stopping lactose-containing products, high-fat meals, and alcohol.

Recurrent or prolonged diarrhea can be associated with anal or perianal skin erosions which increase the risk for anal abscesses, fistulas, or proctitis. Good hygiene should be emphasized. Regular examinations of the perianal region should be performed wherever diarrhea has occurred during treatment with cabozantinib. Infections of the perianal region should be treated per local guidelines.

Table 1: Guidelines for Management of Treatment-Emergent Diarrhea for Cabozantinib

Status	Management
Tolerable Grade 1-2 (duration < 48 h)	
 • Continue with study treatment and consider dose reduction • Initiate treatment with an antidiarrheal agent (e.g., loperamide 4 mg followed by 2 mg after each episode of diarrhea [maximum: 16 mg loperamide daily]) • Dietary modifications (e.g., small lactose-free meals, bananas and rice) • Intake of isotonic fluids 1-1.5 L/day) • Re-assess after 24 hours: 
 - Diarrhea resolving to baseline bowel habits: gradually add solid foods and discontinue or decrease antidiarrheal treatment after 12 h diarrhea-free interval - Diarrhea not resolving: Continue/resume antidiarrheal treatment
Intolerable Grade 2, Grade 2 > 48h, or ≥ Grade 3	
 • Interrupt study treatment • Ask participant to attend clinic • Rule out infection (e.g., stool sample for culture) 
 - Administer antibiotics as needed, (e.g., if fever or Grade 3-4 neutropenia persists > 24 h) • Administer fluids 1-1.5L/day orally or IV, as appropriate for hydration or to correct electrolyte abnormalities • For Grade 3-4 or complicated lower grade diarrhea consider hospitalization and IV hydration • Re-assess after 24 hour • Diarrhea resolving to baseline bowel habits or Grade ≤ 1: 
 - Consider restarting study treatment at reduced dose • Diarrhea not resolving: 
 - Start and or continue antidiarrheal treatment (e.g., loperamide 4 mg followed by 2 mg after each episode of diarrhea [maximum 16 mg loperamide per day - Consider starting second line antidiarrheal or referral to gastroenterologist

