- Grade 4 drug-related amylase or lipase abnormalities require dose delay. Participants should be monitored for development of symptoms or clinical manifestations of pancreatitis.
- Grade 4 drug-related electrolyte abnormalities require dose delay. Electrolyte correction with supplementation/appropriate management should be promptly initiated.

- Grade 4 drug-related neutropenia, lymphopenia, leukopenia, anemia, or thrombocytopenia
- Any adverse event, laboratory abnormality, or intercurrent illness which, in the judgment of the investigator, warrants delaying cabozantinib dosing
- For participants scheduled for major surgery, including dental surgery which may impact bone healing, cabozantinib dosing should be delayed at least 28 days prior to scheduled surgery. The treating physician should use clinical judgment with regard to the risks and benefits of the planned surgical procedure if it is not possible to delay cabozantinib dosing for 28 days prior to the procedure. A delay of cabozantinib dosing of 5 to 7 days is recommended for healing for minor surgery.

As a general approach, all AEs related to cabozantinib should be managed with supportive care when possible at the earliest signs of toxicity. Calcium, magnesium, potassium, and phosphorus should be kept above the lower limits of the laboratory normal values. Please refer to the cabozantinib IB, [Appendix 10](#), and [Appendix 11](#) for additional information regarding dose modifications and AE management.²¹

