7.4.3.2 Criteria to Resume Cabozantinib Treatment

Participants may resume treatment with cabozantinib when the drug-related AE(s) resolve to Grade \leq 1 or baseline value, with the following exceptions:

- Participants may resume dosing in the presence of Grade 2 fatigue
- Participants who delayed dosing due to prolonged QTcF may resume dosing at one reduced dose level once QTcF returns to \leq 500 msec
- Participants who delayed dosing due to UPCr $>$ 2.0 or urine dipstick protein \geq 3+ or urine protein $>$ 2.0 g / 24 may resume dosing at one dose level reduction when UPCr is \leq 2.0 or 24 hour urine protein \leq 2.0 g /24
- Participants who delayed dosing due to Grade 3 hypertension may resume dosing at the same dose or at one dose level reduction, at the discretion of the investigator, when hypertension has improved to Grade \leq 2
- Participants who delayed dosing due to Grade 4 lipase or amylase abnormalities may resume dosing upon resolution to Grade \leq 2
- Participants who delayed dosing due to major surgery should not resume cabozantinib until complete wound healing has taken place. Following cabozantinib resumption, participants should be monitored for wound dehiscence, wound infections, and other signs of impaired wound healing.
- Participants who develop a pulmonary embolism and/or DVT should have study treatment interrupted until therapeutic anticoagulation is established. Treatment with cabozantinib may be resumed in subjects with pulmonary embolism or DVT if it is determined that the event is uncomplicated and that the subject is deriving clinical benefit from cabozantinib treatment and that anticoagulation does not place them at a significant risk that outweighs the benefit of resuming treatment per discretion of the investigator.
- Participants who delayed dosing due to \leq Grade 2 hemorrhage may resume dosing if bleeding is under control (recovered to at least Grade 1 level) and has a low risk of recurrence
- If treatment is delayed $>$ 6 weeks for any reason, the participant must be permanently discontinued from study therapy, except in cases where permission to resume treatment is granted by the BMS Medical Monitor or designee.

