8.1.2 Cabozantinib Dose Discontinuation

Permanently discontinue cabozantinib for participants with any of the following:

- Any requirement for more than 2 cabozantinib dose reductions (ie, reduction to less than 20 mg every other day)
- Any Grade \geq 2 drug-related arterial thromboembolic events, including cerebrovascular ischemia, cardiac ischemia/infarction, peripheral or visceral arterial ischemia
- Any Grade \geq 3 drug-related hemorrhage
- Grade 4 hypertension or persistent Grade 3 hypertension despite optimal medical management and cabozantinib dose reduction
- Drug-related reversible posterior leukoencephalopathy syndrome

- Development of drug-related fistula or GI perforation
- Drug-related nephrotic syndrome
- Any drug-related liver function test (LFT) abnormality that meets the following criteria requires discontinuation:
 - AST or ALT > 8 x ULN.
 - Concurrent AST or ALT > 3 x ULN and total bilirubin >2 x ULN, consistent with potential drug-induced liver injury (see [Section 9.2.7](#)).
- Any Grade 4 drug-related adverse event or laboratory abnormality, with the following exceptions:
 - Grade 4 neutropenia ≤ 7 days
 - Grade 4 lymphopenia or leukopenia
 - Grade 4 amylase or lipase abnormalities that are not associated with symptoms or clinical manifestations of pancreatitis
 - Isolated Grade 4 electrolyte abnormalities that are not associated with clinical sequelae and are corrected with supplementation/appropriate management within 72 hours of their onset
- Any dosing interruption lasting > 6 weeks unless the BMS Medical Monitor or designee is consulted and agrees with the rationale for resuming therapy after a delay > 6 weeks. Note that tumor assessments should continue as per protocol even if dosing is interrupted.
- Any adverse event, laboratory abnormality, or intercurrent illness which, in the judgment of the Investigator, presents a substantial clinical risk to the participant with continued cabozantinib dosing.

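### Protocol Appendix 11 lets cabozantinib restart after drug-related Grade 4 diarrhea, which Section 8.1.2 makes a permanent stop; no text says which governs

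*Protocol*

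**What the plan says.** **Appendix 11 (diarrhea on cabozantinib).** The second row of Table 1 is headed "Intolerable Grade 2, Grade 2 > 48h, or ≥ Grade 3". It tells the site to interrupt study treatment, rule out infection and rehydrate. It names the top grades itself: "For Grade 3-4 or complicated lower grade diarrhea consider hospitalization and IV hydration". If the diarrhea returns to baseline bowel habits or to Grade 1 or lower, the instruction is "Consider restarting study treatment at reduced dose". The introductory text adds: "When the diarrhea is controlled, retreatment with cabozantinib may be acceptable per investigator decision". Neither place sets a grade above which restart is ruled out, and neither mentions Section 8.1.2.

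**Section 8.1.2 (permanent discontinuation of cabozantinib).** One criterion is "Any Grade 4 drug-related adverse event or laboratory abnormality, with the following exceptions". The exceptions are:
- neutropenia of 7 days or less;
- lymphopenia or leukopenia;
- amylase or lipase changes without pancreatitis;
- isolated electrolyte abnormalities that have no sequelae and are corrected within 72 hours.

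**The link between them.** Section 7.4.1.2 refers sites to Appendix 11, along with the investigator brochure and Appendix 10, "for additional information regarding dose modifications and AE management".

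**The concern.** A site managing severe diarrhea would naturally open the diarrhea table, to which the dose-delay section has directed it. If the event is Grade 4 and judged related to cabozantinib, the table offers a restart that Section 8.1.2 forbids. A restart made in good faith would re-expose the participant to a drug the protocol says to stop for good. It would also be a protocol deviation, since Section 9 allows no waivers or exemptions.

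The stakes are participant safety and consistent conduct across sites.

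**Working it through.** No arithmetic settles this; it is a comparison of texts.

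**1. The two rules by type of event**

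| Diarrhea event | Appendix 11 | Section 8.1.2, Grade 4 criterion | Compatible? |
|---|---|---|---|
| Grade 2 (intolerable or over 48 h) or Grade 3 | Interrupt; may restart on recovery | Not triggered | Yes |
| Grade 4, not drug-related | Interrupt; may restart on recovery | Not triggered | Yes |
| Grade 4, drug-related | Interrupt; may restart on recovery | Permanent stop, no exception applies | **No** |

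Table 1 covers treatment-emergent diarrhea without regard to cause, so it has legitimate reason to mention Grade 4. Only the last row of the comparison is in conflict.

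**2. Does any other text say which rule prevails?**
- Section 7.4 lists Section 8 among the places where cabozantinib modifications are set out, but gives it no priority.
- Section 7.4.1.2 cites 8.1.2 three times: for hemorrhage, for AST or ALT above 8 x ULN, and for concurrent transaminase and bilirubin elevation. None of these covers Grade 4 events in general.
- Section 7.4.2.2 cites 8.1.2 only when more than two dose reductions would be needed. Its option to resume at the same dose after an adverse event is limited to Grade 2 or 3, apart from its separate hypertension provision. That fits the intent of 8.1.2 but does not state a Grade 4 rule.
- Section 7.4.3.2 begins "Participants may resume treatment with cabozantinib when the drug-related AE(s) resolve to Grade" 1 or lower, or to baseline. It sets no limit on the worst grade reached and does not cite 8.1.2.
- The general list of mandatory discontinuations in Section 8.1 points to the criteria in 8.1.1 and does not name 8.1.2.
- For sunitinib, Section 7.4.1.3 tells sites to consult Section 8 for discontinuation criteria before resuming after a delay. The cabozantinib text has no such sentence.

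**3. Who is exposed?** Section 8.1.1 stops nivolumab for Grade 3 drug-related diarrhea of any duration. It stops all study drugs when the investigator blames all of them or cannot tell which is responsible. It also requires each drug to be assessed separately and may allow drugs not thought responsible to continue. The main uncovered case is therefore Grade 4 diarrhea attributed to cabozantinib alone. This includes participants on cabozantinib alone after nivolumab stops: Section 7.4.2.2 provides for that state, and Section 5.1 allows cabozantinib to run past 2 years.

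**4. A secondary overlap.** Section 7.4.1.2 names eight Grade 4 laboratory abnormalities as reasons to delay: amylase, lipase, electrolytes, and those in the bullet "Grade 4 drug-related neutropenia, lymphopenia, leukopenia, anemia, or thrombocytopenia". Against the 8.1.2 exceptions:
- excepted outright: 2 (lymphopenia, leukopenia);
- excepted on a condition: 4 (neutropenia, amylase, lipase, electrolytes);
- not excepted: 2 (anemia, thrombocytopenia);
- 2 + 4 + 2 = 8.

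For anemia and thrombocytopenia, the delay bullet alone does not contradict a permanent stop, since dosing can be held while 8.1.2 is applied. The tension appears only when that bullet is read together with the open-ended resume rule in 7.4.3.2.

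**The case against.** The strongest reply is that the texts differ in force. Section 8.1.2 is mandatory, whereas Appendix 11 is titled as guidelines and only permits a restart. A site that does not restart satisfies both. Outside investigator judgment, the delay triggers in 7.4.1.2 for non-laboratory events stop at Grade 3, so Grade 4 diarrhea falls naturally to 8.1.2. Other safeguards exist as well: Section 9 requires immediate safety concerns to be discussed with the sponsor, and under Appendix 3 a life-threatening event is a serious adverse event reportable within 24 hours.

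Most of this stands, and it is why the risk is small. It does not remove the inconsistency: permission to consider a restart is still permission to do what 8.1.2 prohibits, and a reader must infer the precedence.

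Three stronger readings are tempting but unsupported.
- **Three equal conflicts.** A reader might add Grade 4 anemia and thrombocytopenia to diarrhea. The delay bullet says only to hold dosing; it offers no restart, so these are not on the same footing.
- **A size based on dose levels.** A reader might argue that the conflict arises only where a lower dose remains available in Table 7.4.2-1. The introductory text of Appendix 11 allows retreatment without requiring a reduction, so that count does not follow, and it would say nothing about frequency.
- **A flaw in the trial's inference.** Nothing here bears on the PFS or OS analyses.

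**Conclusion.** The point holds as an internal inconsistency that calls for a minor safety correction. For drug-related Grade 4 diarrhea, Appendix 11 permits what Section 8.1.2 forbids, and no text settles the matter. The rest of the cabozantinib text suggests that 8.1.2 is what was intended: where that section means to leave discretion, as with interruptions beyond 6 weeks, it says so, and the Grade 4 criterion contains no such clause.

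No frequency can be attached, because the documents give no incidence of Grade 4 diarrhea or of its attribution to cabozantinib. The conclusion rests on the released text. The sections compared are legible, but the investigator brochure, which 7.4.1.2 also cites, was not available.

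**What to change.** **Main change, Appendix 11.**
- In the second row of Table 1, limit the restart line to Grade 2-3 diarrhea, or Grade 4 diarrhea that is not drug-related.
- Add to that row: *Drug-related Grade 4: permanently discontinue cabozantinib per Section 8.1.2.*
- Add to the retreatment sentence in the introductory text: *except after drug-related Grade 4 diarrhea (Section 8.1.2).*

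**Secondary change, Sections 7.4.1.2 and 7.4.3.2.** Add the reminder that the sunitinib text already carries, so that Section 8 is checked before cabozantinib is resumed. Grade 4 anemia and thrombocytopenia would then follow 8.1.2. If the sponsor means these to be managed by delay, they should be added to the 8.1.2 exceptions instead.

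**Cost.** Wording edits in up to four places, by amendment or administrative letter. No new procedures, data or participants are needed, and the main change leaves 8.1.2 as it is.

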APPENDIX 12 COUNTRY SPECIFIC REQUIREMENTS

COUNTRY SPECIFIC REQUIREMENTS

Country Location	Original language	Country-specific language
Germany, Czech Republic, Romania at all sites where it is mandated by local or country regulations	Section 2 Schedule of Activities, Table 2-1, Screening Procedural Outline, Laboratory Tests	Add “HIV” to the list of laboratory tests
Germany, Czech Republic, Romania at all sites where it is mandated by local or country regulations	Section 6.2 Exclusion Criteria, Exclusion criterion 1 g)	“Known history of testing positive for human immunodeficiency virus (HIV) or known acquired immunodeficiency syndrome (AIDS)” to be replaced with “Positive test for HIV”.
Czech Republic	Section 8.1: Discontinuation from Study Treatment	Second paragraph modified to read: “In the case of pregnancy, the investigator must immediately notify the BMS Medical Monitor/designee of this event. In most cases, the study treatment will be permanently discontinued in an appropriate manner (e.g., dose tapering if necessary for participant safety). Please call the BMS Medical Monitor within 24 hours of awareness of the pregnancy.” The following statement is deleted: “If the investigator determines a possible favorable benefit/risk ratio that warrants continuation of study treatment, a discussion between the investigator and the BMS Medical Monitor/designee must occur.”
Czech Republic, Romania	Section 9.4.1: Clinical Safety Laboratory Assessments	Serology section modified to read: Serum for hepatitis C antibody, HCV RNA, hepatitis B surface antigen (screening only). HIV testing must be performed at sites where mandated by local or country regulations, see Appendix 12)

APPENDIX 13 REVISED PROTOCOL SUMMARY OF CHANGE HISTORY

[REDACTED]

[REDACTED]

[REDACTED]

[REDACTED]

[REDACTED]

This Revised Protocol 01 applies in all countries, at all sites, to all future participants enrolled in the study, and where applicable, to all participants currently enrolled in the study

SUMMARY OF KEY CHANGES FOR REVISED PROTOCOL 01	
Section Number & Title	Description of Change
Title Page and Synopsis Protocol Title	In the Protocol Title, Arm B wording is deleted.
Synopsis and Section 4 Objectives and Endpoints	Arm B wording is deleted. Objectives and endpoints for intermediate/poor risk groups are deleted [REDACTED]
Synopsis and Section 5.1 Design	Arm B wording is deleted. Number of Arms is revised from 3 to 2, and treatment allocation to 1:1. Sample size is revised Favorable risk cap is adjusted up to 25% Schematic is revised Impact of Revised Protocol 01 on Arm B patients is clarified
Synopsis, Table 2-3, and Multiple Sections 5.1, 7, 7.1, 7.1.2, 7.4, 8.1.1, 9, 9.5	A paragraph is added to clarify the impact of Revised Protocol 01 on Arm B patients
Procedural Outline Tables 2-2, 2-3 and 2-4	Tumor Tissue row, Notes column - a paragraph is added to clarify procedures associated with Treatment beyond Progression
[REDACTED]	[REDACTED]
Section 3.1.1 Research Hypothesis	Arm B wording is deleted.
Section 3.2.1.3 Ipilimumab in Renal Cell Carcinoma	Section deleted as no longer relevant
Section 3.2.1.3 Nivolumab Plus Ipilimumab in Renal Cell Carcinoma	[REDACTED] (Section numbering is adjusted from 3.2.1.4 to 3.2.1.3, after deletion of prior section 3.2.1.3)

SUMMARY OF KEY CHANGES FOR REVISED PROTOCOL 01		
Section Number & Title	Description of Change	
Section 3.2.1.4 Cabozantinib Monotherapy in Renal Cell Carcinoma	Paragraph regarding cabozantinib efficacy is updated with ESMO data	
[REDACTED]	Arm B wording is deleted. [REDACTED]	
Section 5.1.1 Data Monitoring Committee	Data Monitoring Committee review after 30 patients are treated for 6 weeks, is added.	
Section 5.2 Number of Participants	Sample size is adjusted	
[REDACTED]	Arm B wording is deleted. Number of Arms is revised from 3 to 2, and treatment allocation to 1:1. Favorable risk cap is adjusted up to 25%	
[REDACTED]	Arm B wording is deleted. Number of Arms is revised from 3 to 2, and treatment allocation to 1:1.	
[REDACTED]	[REDACTED]	
[REDACTED]	Arm B wording is deleted. [REDACTED]	
[REDACTED]	Arm B wording is deleted [REDACTED]	
[REDACTED]	Arm B wording is deleted.	

SUMMARY OF KEY CHANGES FOR REVISED PROTOCOL 01		
Section Number & Title	Description of Change	
Dosing Duration for Nivolumab	With this revised protocol, the option for retreatment on study in subjects who progress after completing 2 years of nivolumab treatment will be removed from the protocol.	
Synopsis and Section 6.2.1a Exclusion Criteria	Exclusion criteria 6.2.1a revises criteria for CNS metastases that are treated and stable, from at least 3 months to at least 1 month	
Section 6.2.1b Exclusion Criteria	Exclusion criteria 6.2.1b adds ‘celiac disease’ as an example external trigger.	
Section 6.2.1o Exclusion Criteria	Exclusion criteria 6.2.1o revises LMWH criteria for DVT and PE, from at least 6 weeks to at least 3 weeks	
Section 6.2.2e Exclusion Criteria	Exclusion criteria 6.2.2e is revised to major surgery less than 6 weeks, nephrectomy less than 4 weeks, prior to randomization, provided complete wound healing and no ongoing post-operative complications.	
Section 6.2.2g Exclusion Criteria	An exclusion is added regarding botanical preparations	
Section 6.2.3f Exclusion Criteria	Exclusion criteria 6.2.3f is clarified	
Section 6.2.3i Exclusion Criteria	Exclusion criteria 6.2.3i adjusts UPCR limit to permit UPCR = 1.5, unless 24-hour urine protein is ≤ 1.5 g	
Section 7.1 Treatment	Clarification of a sentence revising ‘...approximately 30 minutes...’ to read ‘...at least 30 minutes...’. For consistency, the phrase ‘but may be more or less depending on the situation’ is deleted.	
Section 7.4.1.2 Dose Delay Criteria for Cabozantinib	Clarifies that Grade 2 drug-related adverse event or laboratory abnormality (e.g., AST, ALT, total bilirubin) that persists for more than 1 week or worsens despite supportive care management, will delay cabozantinib dosing	

SUMMARY OF KEY CHANGES FOR REVISED PROTOCOL 01		
Section Number & Title	Description of Change	
Section 7.4.1.3 Dose Delay Criteria for Sunitinib	The final paragraph refers the Investigator to the sunitinib label for additional information regarding monitoring of adverse events, in addition to management of adverse events.	
Section 7.4.2.2 Dose Reduction and Escalation for Cabozantinib	Participants with asymptomatic Grade 2 drug-related AST, ALT or total bilirubin elevation, or Grade 3 drug-related lipase or amylase abnormalities that are not associated with symptoms or clinical manifestations of pancreatitis may reduce cabozantinib by one dose level, without delaying dosing, at the discretion of the investigator.	
Section 7.4.3.1 Criteria to Resume Nivolumab and Ipilimumab Treatment	Bullet 4 is deleted: Participants with combined Grade 2 AST/ALT AND total bilirubin values meeting discontinuation parameters (Section 8.1.1) should have treatment permanently discontinued.	
Section 7.4.3.2 Criteria to Resume Cabozantinib Treatment	Addition of a new bullet; Subjects who develop a pulmonary embolism and/or DVT should have study treatment interrupted until therapeutic anticoagulation is established. Treatment with cabozantinib may be resumed in subjects with pulmonary embolism or DVT if it is determined that the event is uncomplicated and that the subject is deriving clinical benefit from cabozantinib treatment and that anticoagulation does not place them at a significant risk that outweighs the benefit of resuming treatment per discretion of the investigator.	
Section 7.7.1	[REDACTED]	
Section 7.7.2.1	[REDACTED] s	
Section 8.1.1	Addition of myocarditis to Nivolumab and or Ipilimumab discontinuation criteria	

SUMMARY OF KEY CHANGES FOR REVISED PROTOCOL 01		
Section Number & Title	Description of Change	
Section 10 Statistical Considerations	
Arm B wording is deleted.
 
Number of Arms is revised from 3 to 2, and treatment allocation to 1:1.
 
The analysis is revised from intermediate/poor risk groups to all risk groups
 
Favorable risk cap is adjusted up to 25%
 
The sample size is adjusted from N=1014 to N=580 randomized.
 
Analysis populations, Efficacy Analysis, Safety Analysis and Interim Analysis are revised accordingly.
	
Appendix 2	Deleted bullets describing records maintained by site	
Appendix 4	Add a barrier method of contraception for patients in Arms A and or B.	
Appendix 7	Corrected status definitions of Zubrod-ECOG-WHO scores	
All	Formatting and typographical corrections
